8.5.4 Adverse events

All AEs will be recorded from Visit 1 (Dose 1) until 28 days after each dose; only unsolicited AEs starting after the first IMP administration will be collected. SAEs will be collected from date of informed consent and throughout the whole trial (i.e., until Visit 14). Medically attended adverse events (MAAE) will be collected until 28 d after each dose.

Solicited AEs (i.e., reactogenicity events) are recorded in the trial subjects' e-diaries and should not be reported as AEs unless the solicited AE meets criteria for an SAE or continue past Day 7 of each IMP dose.

Page 23 of 36 Version: 3.0 Date: 08 MAY 2024

All AEs will be coded using the most recent version of MedDRA® coding system version 25.1 or later and graded for severity using FDA Guidance for Industry: "Toxicity Grading Scale for Healthy Adult and Adolescent Volunteers Enrolled in Preventive Vaccine Clinical Trials"⁴. In case a subject has an AE with missing relationship status, the event will be assumed to be related. No imputation for missing grades will be performed.

If an AE is reported more than once by the same subject for a System Organ Class (SOC) / Preferred Term (PT) the associated AE will be counted once for the SOC / PT under the maximum severity.

All AE summary tables will be sorted alphabetically by SOC and PT within SOC.

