3 OBJECTIVES AND ENDPOINTS

3 OBJECTIVES AND ENDPOINTS					
OBJECTIVES	ESTIMANDS	ENDPOINTS			
Primary objectives					
To describe the safety and tolerability of BNT165b1 vaccination in healthy adults.	 For each DL cohort: Frequency of solicited local reactions at the injection site recorded up to 7 d after each dose. Frequency of solicited systemic reactions recorded up to 7 d after each dose. Proportion of subjects with at least one AE occurring up to 28 d after each dose. Proportion of subjects with at least one MAAE occurring up to 28 d after each dose. Proportion of subjects in each cohort with at least one SAE occurring up to 24 weeks after Dose 3. 	 Solicited local reactions (pain, erythema/redness, induration/swelling) Solicited systemic reactions (vomiting, diarrhea, headache, fatigue, myalgia, arthralgia, chills, and fever) AEs SAEs MAAEs 			
Exploratory objectives					
To describe the humoral immune responses induced by BNT165b1 vaccination at different DLs in healthy adults.	Not applicable	Levels of antigen-specific serum and/or plasma antibodies (total IgG) measured using ELISA and/or similar assays CCI			
CCI					

Page 26 of 82 Version: 4.0 Date: 13 FEB 2023

Abbreviations: AE = adverse event; CCI d(s) = day; DL(s) = dose level(s); ELISA = enzyme-linked immunosorbent assay; IgG = immunoglobulin G; MAAE = medically attended adverse event; SAE = serious adverse event.

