8.2.6.2 Assessments of intensity for systemic reactions

Symptoms of systemic reactions will be assessed as absent, mild, moderate, severe, or potentially life-threatening, according to the grading scale in Table 3.

Any systemic reaction of Grade 3 or higher will be confirmed by the investigator along with an assessment if it meets the definition of Grade 4.

Page 46 of 82 Version: 4.0 Date: 13 FEB 2023

Table 3: Systemic reaction grading scale

	Mild (Grade 1)	Moderate (Grade 2)	Severe (Grade 3) ^a	Potentially life-threatening (Grade 4) ^a
Vomiting	1 to 2 times in 24 h	>2 times in 24 h	Requires intravenous hydration	Emergency room visit or hospitalization for hypotensive shock
Diarrhea	2 to 3 loose stools in 24 h	4 to 5 loose stools in 24 h	6 or more loose stools in 24 h	Emergency room visit or hospitalization for severe diarrhea
Headache	Does not interfere with activity	Some interference with activity	Prevents daily routine activity	Emergency room visit or hospitalization for severe headache
Fatigue / tiredness	Does not interfere with activity	Some interference with activity	Prevents daily routine activity	Emergency room visit or hospitalization for severe fatigue
Myalgia – muscle pain	Does not interfere with activity	Some interference with activity	Prevents daily routine activity	Emergency room visit or hospitalization for severe muscle pain
Arthralgia – joint pain	Does not interfere with activity	Some interference with activity	Prevents daily routine activity	Emergency room visit or hospitalization for severe joint pain
Chills	Does not interfere with activity	Some interference with activity	Prevents daily routine activity	Emergency room visit or hospitalization for severe chills
Fever (oral temperature of ≥38.0°C/≥100.4°F)	38.0°C/100.4°F to 38.4°C/101.1°F	38.5°C/101.2°F to 38.9°C/102.0°F	39.0°C/102.1°F to 40.0°C/104.0°F	>40.0°C/>104.0°F

a. Investigator or medically qualified person confirmation is required.

Source: Based on the US FDA "Toxicity Grading Scale for Healthy Adult and Adolescent Volunteers Enrolled in Preventive Vaccine Clinical Trials".

8.2.7 Subject e-diaries for assessment of reactogenicity (local and systemic reactions) – Trial site personnel and investigator tasks

Subject e-diaries will be issued, trained, and collected by trial site personnel at the visits given in the SoA (Section 1.3).

The trial site personnel will ask/remind the trial subjects to:

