- Record the worst grade for each symptom in the e-diary at approximately the same time every evening on the day of IMP injection and then every day in the evening for a total of seven consecutive days.
- Measure their body temperature using the provided device and record their body temperature in the e-diary every day including the day of IMP injection.
- To assess any solicited local reactions at the injection site as described in Section 8.2.6.1 and solicited systemic reactions as described in Section 8.2.6.2.
- To contact the site immediately in case of severe or potentially life-threatening reactogenicity events.

Clinical Trial Protocol Trial number: BNT165-01 Page 47 of 82 Version: 4.0 Date: 13 FEB 2023

Investigators will review subject-reported e-diary data at the times given in the SoA (Section 1.3).

Only an investigator or medically qualified person is able to confirm Grade 3 or a potentially life-threatening Grade 4 event for recording in the EDC system.

If a trial subject experiences confirmed Grade 4 reactogenicity, the investigator must immediately notify the sponsor and, if it is determined to be related to the administration of IMP, further IMP administration will be discontinued in that trial subject (see Section 7.1).

If a trial subject experiences a potential Grade 3 reactogenicity or higher, the subject must immediately notify the investigator or some other medically qualified person, who will then confirm the grading, the confirmed Grade 4 reactogenicity will be recorded by the investigator as an SAE. Data for solicited Grade 3 or lower events do not need to be reported separately by the investigator as AEs in the EDC system, unless they are reported as an unsolicited event or extends beyond the 7 d.

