10.4.1 Definition of AE

AE definition:

- An AE is any untoward medical occurrence in a trial subject administered a
 pharmaceutical product and which does not necessarily have to have a causal
 relationship with this treatment.
- NOTE: An AE can therefore be any unfavorable and unintended sign (including an abnormal laboratory finding), symptom, or disease (new or exacerbated) temporally associated with the use of a medicinal product, whether or not considered related to the medicinal product.
- Medically attended adverse event is an AE for which the subjects received medical attention defined as hospitalization, or an otherwise unscheduled visit to or from medical personnel for any reason, including emergency room visits.

10.4.1.1 Events meeting the AE definition:

- Any abnormal laboratory test results (hematology or clinical chemistry) or other safety assessments (e.g., ECG, vital signs measurements), including those that worsen from baseline, considered clinically significant in the medical and scientific judgment of the investigator.
- Exacerbation of a chronic or intermittent pre-existing condition including either an increase in frequency and/or severity of the condition.
- Serious AEs occurring after the date informed consent was given (ICF signed and dated) and AEs (non-serious AEs) occurring after first IMP administration.
- Signs, symptoms, or the clinical sequelae of a suspected drug-drug interaction.
- Signs, symptoms, or the clinical sequelae of a suspected overdose of either trial treatment or a concomitant medication. Overdose per se will not be reported as an AE/SAE.

10.4.1.2 Events not meeting the AE definition:

- Any clinically significant abnormal laboratory findings or other abnormal safety assessments which are associated with an underlying disease, unless judged by the investigator to be more severe than expected for the trial subject's condition.
- Medical or surgical procedure (e.g., endoscopy, appendectomy): the condition that leads to the procedure is the AE.
- Situations in which an untoward medical occurrence did not occur or continue (social and/or convenience admission to a hospital).
- Anticipated day-to-day fluctuations of pre-existing disease(s) or condition(s) present or detected at the start of the trial that do not worsen.

Page 67 of 82 Version: 4.0 Date: 13 FEB 2023

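### Non-serious solicited reactions that receive medical attention and resolve by Day 7 have no prescribed route into the primary MAAE proportion, and sites may capture them inconsistently

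*SAP*

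**What the plan says.** Protocol section 3 and SAP Table 2 both list among the primary estimands: "Proportion of subjects with at least one MAAE occurring up to 28 d after each dose". Protocol 10.4.1 defines an MAAE as an AE for which the subject "received medical attention defined as hospitalization, or an otherwise unscheduled visit to or from medical personnel for any reason, including emergency room visits". Nothing in that definition sets solicited reactions aside, and SAP 8.5.4.1 opens the MAAE window on Day 1, inside the seven-day e-diary period.

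The two documents treat the recording of solicited reactions differently:

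- SAP 8.5.4: they "should not be reported as AEs unless the solicited AE meets criteria for an SAE or continue past Day 7 of each IMP dose".
- Protocol 8.2.7: "Data for solicited Grade 3 or lower events do not need to be reported separately by the investigator as AEs in the EDC system". It makes two exceptions: a reaction that is entered as unsolicited, and one that lasts longer than seven days.
- Protocol 8.2.7, for the most severe reactions: "the confirmed Grade 4 reactogenicity will be recorded by the investigator as an SAE".

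SAP 8.5.4.1 bases the AE overview on entries on the Adverse Events eCRF page. The only solicited events it names as included are those that are serious or last beyond Day 7. The e-diary, as described in Protocol 8.2.6 and 8.2.7, collects symptoms, temperature and antipyretic or analgesic use. It is not described as asking about medical visits, and neither document derives MAAEs from it.

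**The concern.** The endpoint definition and the recording rules do not fit together. A reaction can meet the MAAE definition in Protocol 10.4.1 and still, under SAP 8.5.4, be one that should not be entered where MAAEs are counted.

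Such cases are foreseeable. Protocol 12.1 expects reactogenicity within 1 to 3 days of dosing, and Protocol 4.2 reports that reactions to the related vaccine usually resolved within a few days. Typical reactions would therefore not qualify under the Day 7 exception. Protocol 8.2.9 allows reported symptoms to trigger ad hoc site visits.

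At stake is how one primary row is read. A reader who sees a low or zero MAAE proportion for a dose level may conclude that nobody sought care for a reaction. The recording rules do not support that conclusion.

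**Working it through.** The plan states no expected MAAE rate, so there is no figure of its own to reproduce on this point. The check sets the rules side by side and then sizes one omission.

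**Step 1. Which attended reactions reach the AE page?** Take a solicited reaction that starts within the e-diary period and resolves by Day 7. Inputs: the MAAE and SAE definitions (Protocol 10.4.1, 10.4.2), the grading scales (Protocol Tables 2 and 3) and the recording rules (Protocol 8.2.7, SAP 8.5.4).

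| Event | Meets MAAE wording | Prescribed route |
|---|---|---|
| Hospitalization, any grade | Yes | SAE |
| Emergency room visit for severe pain, headache, fatigue, myalgia, arthralgia, chills or diarrhea | Yes | Grade 4, so SAE |
| Emergency room visit for fever of 40.0°C or below | Yes | None; fever is graded on temperature alone |
| Emergency room visit for redness or swelling without the skin damage that defines Grade 4 | Yes | None |
| Unscheduled clinic or urgent-care visit | Yes | None |
| Intravenous hydration for Grade 3 vomiting at an unscheduled visit | Yes | None |

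The last four rows assume that the event is not judged serious on some other ground. Grade 3 vomiting is defined as "Requires intravenous hydration". That makes attendance likely but does not settle it, because the MAAE definition turns on the visit and not on the treatment.

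**Step 2. Size of one omission.** Each cohort has 16 vaccine and 4 placebo subjects (Protocol 4.1.1), and placebo is pooled over three cohorts, 3 × 4 = 12 (SAP 8.1). For a subject with no other MAAE, the shift is 100/n:

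- Dose level: 100/16 = 6.25 points.
- Pooled placebo: 100/12 = 8.33 points.

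**Step 3. Chance that a dose level has at least one such subject.** Let q be the probability that a subject has a non-serious attended solicited reaction resolving by Day 7. The documents give no q, so these values are assumptions. P = 1 − (1 − q)^16:

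- q = 1%: 1 − 0.99^16 = 14.9%
- q = 2%: 1 − 0.98^16 = 27.6%
- q = 5%: 1 − 0.95^16 = 56.0%
- q = 10%: 1 − 0.90^16 = 81.5%

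This is the chance that such a subject exists. Whether the subject is omitted depends on which rule the site follows.

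**Step 4. Scale against sampling error.** Exact (Clopper-Pearson) 95% intervals are 0 to 20.6% for 0/16, 0.2 to 30.2% for 1/16 and 1.6 to 38.3% for 2/16. A shift of one or two subjects lies well inside these intervals. The issue is what the count means, not a reversal of a formal result.

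**The case against.** The best case for the plan has four parts.

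- **Much attended reactogenicity is already captured.** Hospitalization at any grade and the emergency room visits that define Grade 4 are recorded as SAEs. This stands, and it confines the gap to non-serious attendance.
- **The protocol does not forbid entry.** It only says that entry is not needed, and it leaves a route for events reported as unsolicited. The schedule of activities separately asks sites to record MAAEs at visits inside the e-diary period, and SAP 8.5.4.1 analyses whatever is entered on the AE page. This also stands. A reader might infer that every such event is lost and that the MAAE proportion is certainly biased, most at the highest dose level. The documents do not support that; they support possible under-capture that varies by site.
- **The reactions are not hidden.** They appear by dose level and maximum grade in the solicited-reaction tables. Medication for reactions is summarized and procedures are listed (SAP 8.3.2). This stands too, but those tables do not show who sought medical attention, which is what this estimand is meant to count.
- **The e-diary specification and CRF are not among the documents.** Either might hold a medical-attendance field. That cannot be excluded, but neither the protocol nor the SAP describes one or uses it to derive MAAEs.

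A reader might also infer that reactions causing a subject to stop dosing go unreported in the same way. The documents do not bear this out. SAP 8.2 summarizes reasons for treatment and trial discontinuation, and SAP 8.5.1 tabulates why Dose 2 or Dose 3 was not given.

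**Conclusion.** The point holds as a gap between a primary endpoint definition and the rules that feed it. Under the written rules, a non-serious solicited reaction that received medical attention and resolved by Day 7 has no prescribed path into the MAAE count. The stricter SAP wording and the permissive protocol wording leave room for sites to differ.

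Any omission can only lower the count, by 6.25 points per subject in a dose level of 16 if that subject has no other MAAE. How many subjects are affected, and whether they cluster by dose, cannot be worked out from the documents. The 14.9% to 81.5% range rests entirely on assumed rates of 1% to 10%. The trial tests no hypothesis, so the consequence is a primary descriptive row that may understate what its definition promises. That warrants correction because the endpoint is primary and the remedy is small.

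**What to change.** Add one exception to Protocol 8.2.7 and SAP 8.5.4, in matching words: a solicited reaction of any grade that led to medical attention as defined in Protocol 10.4.1 is also entered on the AE page, flagged as solicited, and counted in the MAAE summaries of SAP 8.5.4.1 and 8.5.4.2. Carry the same sentence into the CRF completion instructions. This changes recording only, not the management of subjects.

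If data collection is closed, identify cases from source documents and from the concomitant medication and procedure records where possible, and count them. Where that is not possible, label the endpoint in the tables and report as MAAEs excluding non-serious solicited reactions that resolve by Day 7.

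The cost is a sentence in each document, a few extra AE entries and a slightly higher reported MAAE rate. Retrospective recovery adds a source check and may be incomplete.

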8.5.4.1 Overall summary of adverse events

The number and percentage of subjects reporting the below events will be summarized for the subjects in safety set.

- Unsolicited AEs with onset from Day1 through Day 28 post IMP dose will be summarized for each dose (i.e., 1st dose, 2nd dose, 3rd dose) and regardless of the number of doses received. All events entered on the "Adverse Events" eCRF page with an onset date within the above-mentioned timeframe will be analysed. This includes solicited events that persisted beyond Day 7 after IMP administration or that qualified as an SAE. The following will be analysed:
 - Any unsolicited AEs
 - Related AEs
 - AE of grade >=3
 - Related AEs of grade >=3
 - Any solicited reactogenicity event that continues longer than 7 d post-IMP administration or is an SAE
 - Unsolicited AEs leading to withdrawal of IMP
 - Unsolicited AEs leading to study withdrawal
 - SAEs, with onset from Day 1 through Visit 14. The following will be analysed:
 - Any SAEs
 - Related SAEs
 - SAEs of grade >=3
 - Related SAEs of grade >=3
 - MAAE, with onset from Day1 through 28 days after each dose. The following will be analysed:
 - Any MAAEs
 - Related MAAEs

Page 24 of 36 Version: 3.0 Date: 08 MAY 2024

- MAAEs of grade >=3
- Related MAAEs of grade >=3

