8.3.1 Time period and frequency for collecting AE and SAE information

All AE and SAE information will be collected at the time points specified in the SoA (Section 1.3).

Non-serious AEs will only be collected as of first IMP dose administered while SAEs need to be recorded upon awareness starting once informed consent is given.

Adverse events and medically attended adverse events will be collected until 28 d after each dose and SAEs need to be recorded continuously until Visit 14 (52 weeks post-Dose 3).

Medical occurrences that begin after obtaining informed consent but before the start of trial treatment administration must be recorded on the respective Medical History/Current Medical Conditions section of the CRF and not in the section of the AE unless they qualify as SAEs.

Medical occurrences meeting the criteria for an SAE (see Section 10.4.2) must be reported as SAEs (see Section 8.3.4).

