9.4.2 Safety endpoints

The safety endpoints are defined in Section 3. All safety analyses will be based on the Safety Set, overall, by vaccine DL or placebo.

All AEs will be coded using the most recent version of MedDRA® coding system to get a system organ class and PT for each AE.

Reactogenicity - Subject-reported via the e-diary

Solicited local and systemic reactions (from the subject e-diary) will be summarized. In general, solicited reactions will be analyzed for each immunization, i.e.:

Up to 7 d after each IMP injection

For each injection, the number and percentage of subjects reporting at least one local reaction or systemic reaction (i.e., solicited data collected using subject e-diaries) will be summarized for each of the following types:

- Any local reactions or systemic reactions
- Grade 1, 2, or ≥3 local reactions or systemic reactions

Moreover, the number and percentage of subjects reporting at least one local reaction will be summarized by worst grade.

Unsolicited AEs

The number and percentage of subjects reporting at least one AE (defined in Section 10.4.1) will be summarized by PT nested within system organ class for each of the following AE types:

- Any AE
- Related AE
- · Grade of AE
- Related Grade ≥3 AE
- Any solicited reactogenicity event that continues longer than 7 d post-IMP administration or is an SAE
- Any SAE
- Related SAE

Moreover, the number and percentage of subjects with any AE will be summarized by worst grade by PT nested within system organ class.

Page 57 of 82 Version: 4.0 Date: 13 FEB 2023

Additional safety analyses may be described in the SAP.

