3.1 Objectives, estimands and endpoints

The estimands and endpoints corresponding to each primary and exploratory objective are described in Table 2.

This SAP provides details on the analysis of the primary endpoints.

The analysis of exploratory endpoints is out of scope of this SAP and will be described in a different document.

Table 2: Objective, estimands and endpoints

OBJECTIVES	ESTIMANDS	ENDPOINTS
Primary objectives		
To describe the safety and tolerability of BNT165b1 vaccination in healthy adults.	 For each DL cohort: Frequency of solicited local reactions at the injection site recorded up to 7 d after each dose. Frequency of solicited systemic reactions recorded up to 7 d after each dose. Proportion of subjects with at least one AE occurring up to 28 d after each dose. Proportion of subjects with at least one MAAE occurring up to 28 d after each dose. Proportion of subjects in each cohort with at least one SAE occurring up to 24 weeks after Dose 3. 	 Solicited local reactions (pain, erythema/redness, induration/swelling) Solicited systemic reactions (vomiting, diarrhea, headache, fatigue, myalgia, arthralgia, chills, and fever) AEs SAEs MAAEs

Statistical Analysis Plan (SAP) BNT165-01

Page 7 of 36 Version: 3.0 Date: 08 MAY 2024

OBJECTIVES	ESTIMANDS	ENDPOINTS
Exploratory objectives		
To describe the humoral immune responses induced by BNT165b1 vaccination at different DLs in healthy adults.	Not applicable	Levels of antigen-specific serum and/or plasma antibodies (total IgG) measured using ELISA and/or similar assays CCI
CCI		
Abbreviations: AE = adverse ever	nt: CCI	d(s) = day; DL(s) = dose level(s);
ELISA = enzyme-linked immunos	orbent assay; lgG = immunoglobulin (E = serious adverse event.	G; MAAE = medically attended adverse event;

Page 8 of 36 Version: 3.0 Date: 08 MAY 2024

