8.1.1 General definitions

Baseline is defined as last available value prior to first dose of trial IMP.

Generally, if there are multiple pre-baseline assessments available for a particular day, the assessment that is closest to the day (and time if collected) of the first dose of a trial treatment will be used as the baseline value.

Change from baseline: Unless otherwise specified, this will be calculated as follows:

Change from baseline = post-baseline assessment value – baseline assessment value.

If either the baseline or post-baseline assessment value is missing, the change from baseline is set to missing as well.

Body mass index (BMI) will be calculated as follows:

BMI
$$\left(\frac{\text{kg}}{\text{m}^2}\right) = \frac{\text{Weight (kg)}}{\text{Height(m)}^2}$$

Temperatures collected in °F will be converted to °C as follows:

$$^{\circ}C = (^{\circ}F - 32) * 5/9$$

Duration will be calculated as follows:

• Duration = last observation date - first observation date + 1.

For conversion of days to months or years the following rules will be applied:

- 1 month = 30.4375 days
- 1 year = 365.25 days

Trial Day will be calculated as follows:

- If assessment/onset date < date of first IMP dose, then trial day = assessment date
 date of first IMP dose
- If assessment/onset date >= date of first IMP dose, then trial day = assessment/onset date - date of first IMP dose + 1

That is, trial day 1 indicates the date of first IMP dose.

The day relative to dose 2 or dose 3 will be calculated as follows:

Statistical Analysis Plan (SAP)

BNT165-01

Page 14 of 36

Version: 3.0

Date: 08 MAY 2024

 If assessment/onset >= date of second IMP dose and < date of third IMP dose, then day relative to dose 2 = assessment/onset date - date of second IMP dose + 1

If assessment/onset >= date of third IMP dose, then
 day relative to dose 3 = assessment/onset date – date of third IMP dose + 1

All trial data will be presented at the visit in the visit assigned in the Case Report Form (CRF)/visit assigned in external data. No windowing of data for the purposes of assigning to a visit will occur.

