8.4 Efficacy analysis

There are no efficacy endpoints for this trial.

The primary objective is to describe the safety and tolerability of BNT165b1; the endpoints used for this are described in Section 8.5.2, Section 8.5.3 and Section 8.5.4 below.

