8.5.4.2 Adverse event summaries by SOC, PT and grade

The number and percentage of subjects reporting unsolicited AEs occurring up to 28 days post each dose and regardless of the number of doses will be summarized by PT nested within SOC and by grade. AEs with a missing grade will be presented in the summary table with a grade category of "Missing".

Similar analyses will be provided for:

- SAEs (from Day1 through Visit 14)
- SAEs related to IMP (from Day1 through Visit 14)
- AEs related to IMP (from Day 1 through 28 days post each dose and regardless of the number of doses)
- Solicited AEs that continue longer than 7 d post-dose or are a SAE (from Day 1 through 28 days post each dose and regardless of the number of doses)
- MAAEs (from Day 1 through 28 days after each dose)
- Non-serious AEs (from Day 1 through 28 days post each dose and regardless of the number of doses)
- AEs leading to study withdrawal (any such AEs reported during the study)
- AEs leading to IMP discontinuation (any such AEs reported during the study)

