8.5.4.3 Adverse event summaries by SOC and PT

The number and percentage of subjects reporting the following events will be tabulated by SOC and PT, regardless of the grade:

- SAEs occurring from Day 1 through Visit 14
- Non-serious AEs occurring up to 28 days post each dose and regardless of the number of doses.

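### The primary SAE estimand stops 24 weeks after Dose 3, but every planned SAE table runs to Visit 14, 52 weeks after Dose 3

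*SAP*

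**What the plan says.** SAP Table 2 (section 3.1) gives the primary SAE estimand as "Proportion of subjects in each cohort with at least one SAE occurring up to 24 weeks after Dose 3". Protocol section 3 and the protocol synopsis have the same definition. Protocol 9.4.2 opens its safety analysis with "The safety endpoints are defined in Section 3" and then lists an any-SAE summary without a time window.

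SAP 3.1 states that the SAP covers the analysis of the primary endpoints. SAP 8.4 says where: "the endpoints used for this are described in Section 8.5.2, Section 8.5.3 and Section 8.5.4 below". The SAE summaries in 8.5.4 are:

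- 8.5.4.1 (any, related, grade 3 or higher, related grade 3 or higher): "SAEs, with onset from Day 1 through Visit 14".
- 8.5.4.2 (by SOC, PT and grade): Day 1 through Visit 14, for SAEs and for related SAEs.
- 8.5.4.3 (by SOC and PT): "SAEs occurring from Day 1 through Visit 14".

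Protocol 8.3.1 fixes the end of that period: "SAEs need to be recorded continuously until Visit 14 (52 weeks post-Dose 3". The schedule of activities puts Visit 14 at 365 d after Dose 3 and Visit 13 at 168 d, each with a window of ±10 d. SAP Appendix 1 reports no changes to the protocol-planned analyses.

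**The concern.** The estimand and the tables meant to report it cover different periods. The SAP handles the other event-based components consistently: the AE and MAAE summaries use the 28-day periods of their estimands, and version 2.0 of the SAP changed the MAAE analysis period to follow protocol version 4.0. The SAE component is the one left out of line.

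A programmer following section 8.5.4 would produce a correct table of SAEs through Visit 14 and nothing for the 24-week estimand. The protocol (10.1.6 and 10.1.9) commits the sponsor to posting and publishing results for all primary outcome measures. The posted SAE figure would then either carry the wrong window or be recounted from the listings after the fact, outside the plan. The recount would also lack a rule for subjects who never receive Dose 3. The SAP expects such subjects, since 8.5.1 tabulates reasons for not receiving Doses 2 and 3.

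**Working it through.** **Inputs.** Dose 3 is on Day 183 (SAP Table 3), which is 182 d after Dose 1. The estimand ends 24 weeks, or 168 d, after Dose 3 (SAP Table 2). Visit 14 is 365 d after Dose 3 (schedule of activities). There are 16 vaccinees per cohort and 3 cohorts, so 48 vaccinees.

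**The plan's own timings agree.** 365/7 = 52.1 weeks, matching the 52 weeks stated for Visit 14. 168/7 = 24.0 weeks, so Visit 13 falls nominally on the estimand's cut-off.

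**Window lengths from Dose 1, nominal schedule.**

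- Estimand: 182 + 168 = 350 d (Day 351).
- Tables: 182 + 365 = 547 d (Day 548).
- Difference: 547 − 350 = 197 d, and 197/350 = 56%. With the ±10 d window on Visit 14 the difference is 187 to 207 d.

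**Is there a 24-week SAE summary elsewhere?** The only other rows that mention SAEs are in 8.5.4.1 and 8.5.4.2. They cover solicited events that last beyond 7 d or are serious, within 28 d of each dose. They exclude unsolicited SAEs and mix in non-serious events, so they do not give the primary proportion.

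**Effect of one subject.** 1/16 = 6.25 percentage points for each vaccinee whose first SAE falls in the extra 197 d.

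**Expected size under an assumed rate.** The documents give no SAE rate. With a constant rate r per year and full follow-up, the proportion with at least one SAE by d days is p(d) = 1 − exp(−r·d/365.25). Let Δ = p(547) − p(350). The chance that table and estimand differ for n vaccinees is 1 − (1 − Δ)^n. Figures use unrounded Δ.

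| r per year | p(350) | p(547) | Δ (points) | Extra subjects per 16 | Differ, n = 16 | Differ, n = 48 |
|---|---|---|---|---|---|---|
| 1% | 0.95% | 1.49% | 0.53 | 0.09 | 8.2% | 22.6% |
| 2% | 1.90% | 2.95% | 1.05 | 0.17 | 15.6% | 39.8% |
| 5% | 4.68% | 7.21% | 2.54 | 0.41 | 33.7% | 70.9% |

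The estimand is defined per cohort, so n = 16 is the relevant column. The n = 48 column gives the chance of a discrepancy in at least one of the three dose levels.

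**Day numbering for a corrected cut.** SAP 8.1.1 sets "day relative to dose 3 = assessment/onset date – date of third IMP dose + 1". An event 168 d after Dose 3 therefore has relative day 169.

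**The case against.** The strongest reply is that little is at stake. The trial is descriptive, with no hypotheses. The longer window contains the shorter one, so no post-dose SAE inside the estimand period is hidden and any error is towards reporting more. SAEs are collected to Visit 14 and listed (SAP 8.5.4.4), and with 60 planned subjects a recount is short. If no subject has a first SAE after week 24, the two proportions are identical; under the 2% to 5% rates that has a probability of 66% to 84% in a cohort of 16. All of this stands, and it limits the weight of the point. It does not supply the missing table.

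The rates are assumptions, and at 1% per year the chance of a difference in a cohort falls to about 8%. Visit 14 can also be an early-termination visit, and subjects who leave before week 24 add no extra time. Both are fair, so the firm figures are the 197 d and the 6.25 points.

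It can also be said that 24 weeks appears only in the estimand column of protocol section 3, and that protocol 9.4.2 plans its any-SAE summary with no window, so the Visit 14 tables do not clearly depart from the protocol. That weakens the argument from Appendix 1. The contradiction remains inside the SAP, between Table 2 and section 8.5.4.

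Finally, the AE row of 8.5.4.1 ends at Day 28, which could be one day short of 28 d after dosing if the day-numbering convention of 8.1.1 applies. This is a side issue: the AE summaries in 8.5.4.2 and the MAAE rows use 28 days after each dose.

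**Conclusion.** The concern holds and should be fixed. The mismatch follows from the text and from the 197 d difference on the nominal schedule, and needs no assumption. Its numerical effect does rest on an assumed SAE rate. At a constant 2% to 5% per year with full follow-up, the expected tabulated proportion is 3.0% to 7.2% where the estimand would be 1.9% to 4.7%, and the two would differ in a given cohort with probability 15.6% to 33.7%. The direction is known: the table equals or overstates the estimand for post-dose SAEs. What is missing is a planned analysis of one primary estimand. The data are adequate, and no error rate, sample size or dose decision is affected. The documents do not say which window was intended.

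**What to change.** Either of two changes resolves it.

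1. **Keep the 24-week estimand.** In SAP 8.5.4.1 to 8.5.4.3, add summaries of SAEs and related SAEs with onset from Day 1 through 168 d after Dose 3, and label the any-SAE row as the primary SAE summary. The related-SAE rows go beyond the estimand but parallel the existing tables. Cut by onset date, at relative day 169 or earlier under SAP 8.1.1. Do not cut at Visit 13, because its ±10 d window would vary the period between subjects. State the cut-off for subjects who do not receive Dose 3, for example the nominal equivalent, Day 351. Keep the Visit 14 tables as supportive.
2. **Move the estimand to Visit 14.** Amend the sentence in protocol section 3, the protocol synopsis and SAP Table 2, and record the change in SAP Appendix 1.

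The first option costs one additional cut of tables already planned. The second costs an aligned sentence in both documents and an appendix entry. Neither needs new data.
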